### **Visit schedule and assessments**

See schedule of assessments, Appendix 2

### **Enrollment**

Subjects who may qualify for this study will be identified in the context of clinical care at the participating centers. Such eligible patients may receive a copy of the informed consent form at the time of their clinic visit. Recruitment may also occur through local promotional opportunities (doctor's programs, patient education programs). Patients may contact the participating centers without clinic visitation after reading a notice about the study on the centers' websites or other online postings, or after referral from an outside medical practitioner for study consideration. Such subjects will be offered the chance to undergo a telephone screening using an institutional review board (IRB) approved telephone screening text. Subjects will be requested to send pertinent outside medical records for chart review by the principal investigator and be scheduled for a screening visit.

### **Screening Visit**

At this visit, subjects will be given ample time to read, review and ask questions about the study and the content of the informed consent form. After subjects have signed the informed consent form, they will undergo the following assessments:

- Review of Medical History
- Review of MS History
- Study Eligibility (Inclusion/Exclusion)
- Review of Concomitant Medications
- Physical Examination
- Vital Signs: Blood Pressure, Heart Rate and Temperature
- General and Neurological Evaluation
- Expanded Disability Status Scale (EDSS)
- Laboratory Testing: Complete Blood Count and Comprehensive Metabolic Panel
- Urine Pregnancy Testing for Female Subjects of Childbearing Potential

---

- Urine Analysis, including Culture and Sensitivity for Subjects Reporting Dysuria, Fever and/or Abdominal Pain (at the discretion of the principal investigator)
- Post-void Residual Urine Volume Using Ultrasound Scanner
- Subject Diary Training
- Void Volume Measurement Training

Subjects who meet all inclusion criteria will receive a diary with instructions to record information in their diaries for 72 continuous hours prior to Baseline Visit, during the screening period. Subjects will receive a urine receptacle (“hat” or hand-held urinal, patient preference) and will be trained on how to measure urine volume and record in diary whenever possible during the 72 hour diary period.

### **Baseline Visit**

This visit will be scheduled 7 to 14 days post Screening Visit. The following assessments will be performed:

- Study Eligibility (Inclusion/Exclusion)
- Review of Concomitant Medications
- Adverse Event Assessment
- Vital Signs: Blood Pressure, Heart Rate and Temperature
- Physical Examination (if deemed necessary by investigator)
- Subject Diary Review

Subjects who meet all inclusion criteria will complete the following assessments:

- Qualiveen Questionnaire - pages #1-6 & #9-10 (pages #7-8 are N/A)
- Subject Global Impression
- Bladder Management Difficulties Questionnaire – Short Form (SCI-QOL v1.0)
- Bowel Management Difficulties Questionnaire – Short Form (SCI-QOL v1.0)
- Pelvic Floor Exercise Adherence Question
- Pelvic Floor Exercise Presentation
- Randomization to Group A or Group B
- Drug Dispensing and Training
- Subject Diary Training (if needed)
- Void Volume Measurement Training (if needed)

### **Phone Visit 1**

Study staff will contact each subject 28-32 days post Randomization Visit. The following assessments will be performed:

- Adverse Event Assessment
- Prompting to Resume Subject Diary
- Subject Diary Training (if needed)
- Void Volume Measurement Training (if needed)

Subjects will be instructed to complete the 72 continuous hours of diary entries prior to the Titration Visit. Study staff will reconfirm scheduled dates for follow-up study visits.

### **Titration Visit**

This visit will be scheduled 35-40 days post Randomization Visit. The following assessments will be performed:

---

- Review of Concomitant Medications
- Adverse Event Assessment
- Vital Signs: Blood Pressure, Heart Rate and Temperature
- Physical Examination (if deemed necessary by investigator)
- Urine Pregnancy Testing for Female Subjects of Childbearing Potential (if deemed necessary by investigator)
- Subject Diary Review
- Qualiveen Questionnaire - pages #1-6 only
- Subject Global Impression
- Bladder Management Difficulties Questionnaire – Short Form (SCI-QOL v1.0)
- Bowel Management Difficulties Questionnaire – Short Form (SCI-QOL v1.0)
- Pelvic Floor Exercise Adherence Question
- Subject Diary Training (if needed)
- Void Volume Measurement Training (if needed)
- Drug Dispensing and Training
- Drug Return and Accountability
- Up-Titration Option Question

Subjects may receive increased dose of 50mg of MBG or matching placebo, or remain at 25mg of MBG or placebo, at their discretion and in consultation with the investigator.

### **Phone Visit 2**

Study staff will contact each subject 70-74 days post Randomization Visit. The following assessments will be performed:

- Adverse Event Assessment
- Prompting to Resume Subject Diary
- Subject Diary Training (if needed)
- Void Volume Measurement Training (if needed)

Subjects will be instructed to complete the 72 continuous hours of diary entries prior to the Final Visit. Study staff will reconfirm scheduled dates for follow-up study visits.

### **Final Visit**

This visit will be scheduled 74-82 days post Randomization Visit. The following assessments will be performed:

- Review of Concomitant Medications
- Adverse Event Assessment
- Vital Signs: Blood Pressure, Heart Rate and Temperature
- Physical Examination (if deemed necessary by investigator)
- Urine Pregnancy Testing for Female Subjects of Childbearing Potential (if deemed necessary by investigator)
- Subject Diary Review
- Qualiveen Questionnaire - pages #1-6 only
- Subject Global Impression
- Bladder Management Difficulties Questionnaire – Short Form (SCI-QOL v1.0)
- Bowel Management Difficulties Questionnaire – Short Form (SCI-QOL v1.0)
- Pelvic Floor Exercise Adherence Question
- Drug Return and Accountability

**Unscheduled Visits**

Subjects may return to the clinic for safety evaluation or to receive additional study medication as needed.

**Laboratory tests**

Screening blood testing will include complete blood count and comprehensive metabolic panel. At screening, subjects reporting dysuria, fever or abdominal pain will undergo urine analysis, culture and sensitivity at the discretion of the principal investigator. Urine pregnancy testing will be performed at Screening Visit and office visits thereafter, as indicated by female fertility status and as deemed necessary by investigator.

**Screen failures / Rescreening**

Subjects who screen fail due to not meeting inclusion criteria or due to certain exclusions, e.g. presence of urinary tract infection, may rescreen in 30 days at the discretion of the investigator.

**Early Termination**

Criteria for early termination include, but are not limited to < 36 hours of time covered in a bladder diary, poor adherence to study medication (less than 70% of study medication consumed), safety issues related to study-related or non-study related adverse events, and at the request of the subject or at the discretion of the investigator.

**Efficacy Assessment****Primary Outcome Measure**

Average daily OAB-SCS total score based on OAB SCS at Final Visit vs. Baseline Visit. Every toilet void or incontinence episode will be recorded in a diary based on the OAB-SCS system: 1 = no urgency (normal voiding); 2 = mild (could postpone voiding for as long as necessary without fear of incontinence); 3 = moderate (could postpone voiding for a short while without fear of leakage); 4= severe (could not postpone, had to rush to the toilet); 5= urgency incontinence (could not make it to the toilet without some leakage). Every incontinence episode is scored as 5. Each voiding event is multiplied by the score for the event and then all events are summed to generate a total daily OAB-SCS cumulative score. Each daily total score is averaged to generate the Average daily OAB-SCS total score. For incomplete days (e.g. went out for 6 hours and forgot to record voids) the sum score will be adjusted as follows: total score over 24 hours X 24 / actual # of hours included in documentation (see reference Zinner et al).

**Secondary Outcome Measures based on diaries compared to Baseline Visit:**

- Average daily OAB-SCS total score based on OAB SCS reviewed at Titration Visit
- Titration Visit and Final Visit mean number of micturition/day\*
- Titration Visit and Final Visit mean number of incontinence episodes/day\*
- Titration Visit and Final Visit mean volume voided/micturition\*

\*missing blocks of time will not be included in the scoring

**Secondary Outcome Measures based on Titration Visit and Final Visit compared to Baseline Visit:**

- Qualiveen Questionnaire
  - The English version of the Qualiveen has been found to be a valid and responsive measure of bladder function in MS.24. Site will use pages

---

#1-6 & #9-10 at baseline and only pages #1-6 at other visits. Pages #7-8 will not be used as they are not applicable.

- Subject Global Impression
  - This is a single question: "How would you rate your level of bladder control during the past week?" Please circle your choice:
    - Extremely good, Quite good, Better than average, Average, Below Average, Quite bad, Extremely bad"
- Pelvic Floor Exercise Adherence Question
  - This is a single question: "How many days did you perform pelvic floor exercises during the past two weeks? Please circle your choice:
    - Never, 1 day, 2 days, 3 days, 4 days, 5 days, 6 days, 7 days, more than once a day"
- Bladder Management Difficulties Questionnaire – Short Form (SCI-QOL v1.0)
  - 8 multiple choice questions

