## Protocol Summary

STUDY DRUG	Mirabegron 25-50mg daily
TITLE	Pilot study of mirabegron and behavioral modification including pelvic floor exercise for overactive bladder in multiple sclerosis ( MIRROR )
STUDY OVERVIEW	
A multi-center, randomized 1:1 placebo controlled 10-week study of mirabegron as add-on therapy to an educational intervention on behavioral modification including pelvic floor exercise (BM-PFE) to a cohort of 40 MS subjects with overactive bladder (OAB).
 
Active drug will be mirabegron 25mg daily with optional up-titration to 50mg daily after approximately 5 weeks. Subjects will be randomized at the Baseline Visit based on recordings in a voiding diary kept for 72 continuous hours in the screening period.
 
Voiding diaries of a 72 hour period each will be utilized during the screening period, between Phone Visit 1 and Titration and between Phone Visit 2 and Final Visit. In the diaries, subjects will record the time of each micturition and/or urgency episode, urine volume with each void (when available), any episode of incontinence, and the severity of urgency (Overactive Bladder Symptom Composite Score, OAB-SCS): 1 = no urgency (normal voiding); 2 = mild (could postpone voiding for as long as necessary without fear of incontinence); 3 = moderate (could postpone voiding for a short while without fear of leakage); 4= severe (could not postpone, had to rush to the toilet); 5= urgency incontinence (could not make it to the toilet without some leakage) Each voiding event is multiplied by the score for the event and then all events are summed to generate a total daily OAB-SCS cumulative score).
 
Primary outcome will be average daily OAB-SCS total score, Final Visit vs. Baseline. This accounts for the frequency, urgency and incontinence components of OAB.

RATIONALE	This design will demonstrate the effects of behavioral modification, including pelvic floor exercise on OAB through the placebo arm of the study. Adding mirabegron may yield greater results than BM-PFE alone. The standard starting dose is 25mg daily. An optional up-titration to 50mg is included, since some patients may respond better to the higher dosage. This titration will occur at about 5 weeks to allow a balanced period of time for recording response to the two dosages.
STUDY HYPOTHESIS	Treatment with Mirabegron will improve urinary urgency control beyond that achieved with pelvic floor exercises alone.

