	
 
Concurrent use of thioridazine (Mellaril® or Mellaril-S®), flecainide (Tambocor®), propafenone (Rythmol®) or digoxin (Lanoxin®)
 
Concurrent use of antimuscarinics: oxybutynin (Ditropan®, Ditropan XL®), tolterodine (Detrol®, Detrol LA®), fesoterodine extended-release (Toviaz®), solifenacina (Vesicare®), trospium (Sanctura®, Sanctura XR®), darifenacina extended release (Enablex®)
 
Screening estimated glomerular filtration rate (eGFR) < 60, AST or ALT > 2x upper limit of normal
 
Any other serious and/or unstable medical condition
 

NO. OF SUBJECTS	N= 40. This will include 20 subjects taking mirabegron and 20 subjects taking placebo.
EFFICACY (Outcome measures)	
Primary Outcome Measure:
 
 
Primary outcome will be Average daily OAB-SCS total score, Baseline vs. Final Visit
 
 
Secondary Outcome Measures based on voiding diary, compared to Baseline:
 
 
Titration Visit: Average daily OAB-SCS total score
 
Titration and Final Visit: A) mean # of micturitions/day; B) Mean number of incontinence episodes/day; C) Mean volume voided/micturition
 
 
Secondary Outcome Measures based on the following assessments at Titration Visit and Final Visit compared to Baseline:
 
 
Qualiveen Questionnaire
 
Subject Global Impression (single question)
 
PFE adherence question
 
Bladder Management Difficulties Questionnaire – Short Form (SCI-QOL v1.0)
 
 
Exploratory Outcome Measures based on the following assessments at Titration Visit and Final Visit compared to Baseline:
 
 
Bowel Management Difficulties Questionnaire – Short Form (SCI-QOL v1.0)
 

STATISTICAL METHODS	See Statistics section

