**Behavioral Modification with Pelvic Floor Exercise (BM-PFE) Educational Material**

We will utilize a 20 minute presentation, written by a physical therapist, utilizing a power point presentation. Slides will include images such as pelvic floor anatomy as well as

---

outlines of key points. Participants will be given a paper copy of the power point presentation to take home for reference and to help them with a home bladder exercise regimen.

The following topics are part of this power point presentation:

- Bladder health: What's normal?
- Bladder dietary irritants
- Bladder retraining and urge delay techniques
- Pelvic floor anatomy and function
- How to perform a "Kegel"
- "Kegel" home exercise program
- Pelvic floor exercises with functional activities
- Maintaining your home exercise program

Subjects will have the opportunity to ask the study physician follow-up questions as needed.

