#### **Exploratory Outcome Measures based on Titration Visit and Final Visit compared to Baseline Visit:**

- Bowel Management Difficulties Questionnaire – Short Form (SCI-QOL v1.0)
  - 9 multiple choice questions

Questionnaires will be administered by the research coordinator or study nurse. See Schedule of Assessments above for timing of testing.

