## Statistical Analysis

Demographics and baseline disease characteristics, including age, gender, MS type and duration of disease, level of disability (EDSS), and disease modifying therapy status will be compared between study groups.

Summary and analysis of primary and secondary outcome measures will include

1. Summary statistics (n, mean, standard deviation, median, minimum and maximum) at baseline and week 5 and week 10 by treatment
2. Summary of % change from baseline to week 5 and 10.
3. Significance testing

For the primary outcome measure, Average daily OAB-SCS, each voiding event is multiplied by the score for the event and then all events are summed to generate a total daily OAB-SCS cumulative score. Each daily total score is averaged to generate the Average daily OAB-SCS total score. For incomplete days (e.g. went out for 6 hours and forgot to record voids) the sum score will be adjusted as follows: total score over 24 hours X 24 / actual # of hours included in documentation (see reference Zinner et al).

Mean OAB-SCS score at Baseline Visit will be included in the model as an independent variable. The primary time points for all comparative measures will be Baseline Visit, Titration Visit and Final Visit. Outcome measures will be compared between groups using analysis of covariance (ANCOVA) or other method. Demonstration of superiority will depend on achieving statistical significance for the primary endpoint. Level of significance will be defined as  $p=0.05$ . All statistical tests will be two-sided. Statistical assistance will be provided by a statistician consultant whose company is contracted with EvergreenHealth and whose services we have used on two recent MS studies.

Aggregate, de-identified data from the Bladder and Bowel Management Difficulties Short Form Questionnaires (SCI-QOL v1.0) will be shared with the University of Washington in Seattle, WA. This will be done as a courtesy for giving the investigator permission to use these questionnaires in this protocol.

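### The exercise adherence question covers 14 days, but its day options stop at 7, so once-daily exercise on 8 to 14 days cannot be recorded

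*Combined protocol and SAP*

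**What the plan says.** The section on secondary outcome measures at the Titration and Final Visits defines the adherence item as a single question: "How many days did you perform pelvic floor exercises during the past two weeks? Please circle your choice". The printed answers are "Never, 1 day, 2 days, 3 days, 4 days, 5 days, 6 days, 7 days, more than once a day". The Protocol Summary lists the item among the secondary outcomes ("PFE adherence question"), and the visit sections schedule it at the Baseline, Titration and Final Visits.

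For primary and secondary outcomes, the Statistical Analysis section plans "Summary statistics (n, mean, standard deviation, median, minimum and maximum) at baseline and week 5 and week 10 by treatment", then percentage change from baseline and significance testing. On method it says "Outcome measures will be compared between groups using analysis of covariance (ANCOVA) or other method". It gives no scoring or coding rule for this item.

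Two other places might have settled the meaning but do not:

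- The educational material section lists a home programme, including the topic "Maintaining your home exercise program", without stating how often subjects are to exercise.
- The exploratory outcomes section says "Questionnaires will be administered by the research coordinator or study nurse", with no instruction on how to read or record this question.

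**The concern.** The question and its answers are on different scales. The stem asks for a number of days out of 14. The answers give days out of 7 and then a number of sessions per day. This causes three problems:

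- Once-daily exercise on 8 to 14 days has no true answer, so half the days and every day cannot be told apart.
- The last option overlaps the day options. Two sessions a day on 3 days fits both the 3-day option and the last one.
- The last option has no day value, so a mean, standard deviation or percentage change in days is undefined without a coding rule.

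This matters because the item is the only measure of exercise adherence described; the Treatment Compliance section covers returned medication only. The Rationale says "This design will demonstrate the effects of behavioral modification, including pelvic floor exercise on OAB through the placebo arm of the study". To interpret what happens in that arm, a reader needs to know how much exercise was done, and this item describes that poorly at the higher levels. Any comparison of uptake between arms is limited in the same way.

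**Working it through.** The plan states no figure on this point, so there is none to reproduce. The check has a part that needs no assumption and an illustration that does.

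**From the documents alone**

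- Possible day counts in a 14-day window: 0 to 14, which is 15.
- Counts with an option: 0 (never) and 1 to 7, which is 8.
- Counts without an option: 15 − 8 = 7, namely 8 to 14.
- Highest day count that can be recorded: 7/14 = 50% of the window.
- Two readings of an answer of 5 days: 5/14 = 36%, or 5/7 = 71% if the subject takes the options to mean one week. These are shares of days, not of a prescribed amount, because no exercise frequency is stated.
- Percentage change: a baseline answer of never gives a denominator of 0, so the quantity is undefined for that subject.

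**Illustration (assumed uptake)**

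The documents give no expected uptake, so the mean number of exercise days m is varied from 4 to 10 of 14. Exercise is assumed to be once a day, and a subject with 8 or more days is assumed to circle 7. Let X be the true number of days; the recorded value is min(X, 7). Two distributions are used:

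- A: X ~ Binomial(14, m/14), with independent days and the same propensity for all subjects.
- B: beta-binomial with the same mean and intraclass correlation 0.3, so that subjects differ in propensity.

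| True mean m | P(X ≥ 8), A | P(X ≥ 8), B | Recorded mean, A | Recorded mean, B |
|---|---|---|---|---|
| 4 | 0.024 | 0.197 | 3.97 | 3.38 |
| 6 | 0.208 | 0.368 | 5.66 | 4.69 |
| 8 | 0.611 | 0.562 | 6.66 | 5.69 |
| 10 | 0.926 | 0.750 | 6.97 | 6.38 |

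Subtracting recorded means shows what a true difference of 2 days between arms would look like:

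| True means | Recorded difference, A | Recorded difference, B |
|---|---|---|
| 4 v 6 | 1.69 | 1.31 |
| 6 v 8 | 1.00 | 1.00 |
| 8 v 10 | 0.31 | 0.69 |

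The 1.00 under both distributions follows from symmetry: 6 and 8 lie equally far from 7, the midpoint of the window. For the same reason the 4 v 6 and 8 v 10 results add up to 2 under each distribution. The three rows are therefore not independent evidence. They show the direction and rough size of the loss: modest at low uptake and large at high uptake.

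**The case against.** The strongest objection is about weight. Nothing in the plan depends on this item: it is not an eligibility criterion, a model covariate or a reason for early termination. Both arms receive the same education, so the fault does not in itself favour either arm. Never and 1 to 7 days can be recorded as asked, and the answers can be tabulated or analysed ordinally. The effect of the behavioural programme in the placebo arm would be read from bladder outcomes, not from this question. All of this stands and limits the consequence, but it does not give a subject with 8 to 14 days a correct answer. Interpreting the placebo arm is still harder without a usable measure of exercise.

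A second objection is that the last option sits above 7 days, so intensive exercisers can be recorded. This is partly right. The ceiling is on the count of days, and subjects with several sessions a day do have an option, although an overlapping one. Once-daily exercisers on more than 7 days do not.

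A third objection is that the illustrative figures rest on assumed uptake and one assumed response. That is correct. Subjects might instead circle the last option, skip the item or answer for one week, and the plan anticipates no difference in uptake between arms. The uncovered counts and the two readings of 5 days need no such assumption.

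Finally, missing coding rules are a wider feature of this plan; the Subject Global Impression has no numeric code either. What is particular to this item is the change of scale within one list of answers.

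**Conclusion.** The concern holds. As written, the item has no correct answer for 7 of the 15 possible day counts, does not fix the meaning of its day options, and ends in a category that cannot enter the planned means without a rule. This follows from the text alone, and no other section repairs it.

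The practical size cannot be fixed from the documents. Under the assumptions above, the share of subjects on 8 to 14 days runs from 2% to 93% (independent days) or 20% to 75% (subjects differing) as mean uptake goes from 4 to 10 days. The item should be corrected because it is a named secondary outcome and the only exercise-adherence measure. The fault does not touch the primary OAB-SCS comparison and is not in itself a source of bias between arms.

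**What to change.** Make the recall window and the options agree: either one week with 0 to 7 days, or two weeks with 0 to 14 days. The documents do not show which was intended, so the sponsor must say. Under either choice every day count has exactly one answer (8 of 8, or 15 of 15, against 8 of 15 now). Move sessions per day to a separate item. In the Statistical Analysis section, state that days are analysed as a count and how each answer is coded.

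The cost is a minor form change with notification to the IRB. The downside is that answers already collected on the present wording cannot be pooled with the new ones; tabulate them separately in their nine printed categories. If collection is complete, the coding rule and that separate tabulation are still worth having, but the missing day counts cannot be recovered.
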